6.3 Rules and Definitions for Calculated Variables

The following sections describe the identification of the ITT and PP patients and the calculation of the primary endpoint of clinical success.

6.3.1 Intent-to-treat patients

A subject is in the ITT cohort if the subject has signed and dated the ICF.

Valid Data Sources

- Screening Form

Valid Data Points from the Baseline Form:

- “Informed Consent Signature Date”

Analysis approach:

- **Include** a subject in the ITT cohort if the “Informed Consent Signature Date” is complete for all of day, month, and year
- **Exclude** a subject from the ITT cohort if the “Informed Consent Signature Date” if any or all of day, month, or year are missing.

6.3.2 Per-protocol patients

A subject is in the PP cohort if the subject is in the ITT cohort and at least one specimen was obtained using the iNod System.

Valid Data Sources

- ITT cohort subjects
- iNod Diagnostic Procedure Form

Valid Data Points:

- ITT cohort subjects
- iNod Diagnostic Procedure Form:

- “Was a sample obtained?”

Analysis approach:

- **Include** a subject in the PP cohort if **all the following conditions are met:**
 - Subject is in the ITT cohort
 - “Was a sample obtained?” is “Yes”
- **Exclude** a subject from the PP cohort if **one of the following conditions are met:**
 - Subject is not in the ITT cohort
 - “Was a sample obtained?” is “No” or missing

6.3.3 Restricted Per-protocol patients

A subject is in the rPP cohort if the subject is in the PP cohort, the ICF was executed properly, and all eligibility criteria were met.

Valid Data Sources

- PP cohort subjects
- Screening Form
- Protocol Deviation Form

Valid Data Points:

- PP cohort subjects
- Screening Form:
 - “Was all protocol specific entrance criteria met for this subject?”
- Protocol Deviation Form:
 - Protocol Deviation Category

Analysis approach:

- **Include** a subject in the rPP cohort if **all the following conditions are met:**
 - Subject is in the PP cohort
 - “Was all protocol specific entrance criteria met for this subject?” is “Yes”
 - The subject does not have a Protocol Deviation form where “Protocol Deviation Category” has response “Informed Consent”
- **Exclude** a subject from the rPP cohort if **one of the following conditions are met:**
 - Subject is not in the PP cohort
 - “Was all protocol specific entrance criteria met for this subject?” is “No” or missing
 - The subject has a Protocol Deviation form where “Protocol Deviation Category” has response “Informed Consent”

6.3.4 Primary endpoint

The primary endpoint is clinical success defined as the iNod System’s ability to acquire adequate specimens of cellular matter suitable for the cytologic evaluation of targeted lung lesions, under real-time visualization.

Valid Data Sources

- PP cohort subjects
- iNod Diagnostic Procedure Form

Valid Data Points

- PP cohort subjects
- iNod Diagnostic Procedure Resection form: “If yes, was it adequate for Rapid On-Site Evaluation (ROSE) Diagnosis/Cytology?” following the question “Was a sample obtained?” on the same form

Analysis approach:

- Include subject in the **denominator** if **both of the following conditions are met**:
 - Subject is in the PP cohort
 - “If yes, was it adequate for Rapid On-Site Evaluation (ROSE) Diagnosis/Cytology?” is answered “Yes” or “No”
- Include subject in the **numerator** if **both of the following conditions are met**:
 - Subject is in the PP cohort
 - “If yes, was it adequate for Rapid On-Site Evaluation (ROSE) Diagnosis/Cytology?” is answered “Yes”

REVISION HISTORY

Document Revision Number	Template Number and Version	Section	Change	Reason for Change
AA	90702621, AC	All	Original version of the SAP	

Boston Scientific
iNod Feasibility SAP
91154618 Rev/Ver AA
Page 11 of 11

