22. BIBLIOGRAPHY	42
23.2. Definitions	44

Table of Tables

Table 6.1-1: Inclusion Criteria	16
Table 6.2-1: Exclusion Criteria.....	17
Table 8.1-1: Data Collection Schedule	19
Table 8.8-1: Source Documentation Requirements	223
Table 17.1-1: Safety Reporting Definitions.....	34
Table 17.2-1: Criteria for Assessing Relationship of Study Device to Adverse Event	36
Table 17.3-1: Investigator Reporting Requirements.....	36
Table 23.1-1: Abbreviations	43
Table 23.2-1: Definitions	44

Boston Scientific
iNod Feasibility Clinical Protocol
91122035 Rev/Ver AA
Page 10 of 44

1. Introduction

This protocol is a traditional feasibility study for the sampling of a peripheral pulmonary lesion in the setting of a suspicion of lung cancer. Standard of practice radial endobronchial ultrasound (R-EBUS) transbronchial needle aspiration (TBNA) is visualizing a peripheral lesion on R-EBUS, locking the placement of the access sheath, removing the ultrasound catheter from the access sheath and then blindly advancing a sampling device to acquire cellular matter for cytologic evaluation. The iNod system performs the same procedure with one fewer device exchange. It provides real-time visualization of the biopsy needle and target peripheral pulmonary lesions during tissue acquisition. The ultrasound probe is not retracted in advance of the sampling maneuver and the sampling is completed under direct visualization. Compared to current standard of care methods for transbronchial sampling of pulmonary lesions, this approach is not expected to add additional risk. Tissue sampling under real-time visualization may improve the efficiency of tissue sampling.

Lung cancer is the most common cancer worldwide; accounting for 1.8 million new cases and 1.6 million deaths in 2012.¹ Lung CA is also the leading cancer killer in both men and women in the United States.² The number of deaths caused by lung cancer has increased approximately 3.5 percent between 1999 and 2012 from 152,156 to 157,499. In 2012, there were 86,740 deaths due to lung cancer in men and 70,759 in women.² The five year survival rate for lung cancer is 54 percent for cases detected when the disease is still within the lungs. However, only 15 percent of lung cancer cases are diagnosed at an early stage. For distant tumors (spread to other organs) the five-year survival rate is only 4%.³

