The iNod system enables real-time visualization and biopsy of peripheral pulmonary lesions by displaying an ultrasound image of the lesion and needle simultaneously. Intended conditions of use are within a pulmonary endoscopy suite or a surgical suite. The iNod System consists of three components (and accessories) that are either identical to or slightly different in design to existing commercially available devices:

- The **iNod Biopsy Needle** is a modified design of the commercially available 25 gauge BSC Expect Slimline Endoscopic Ultrasound Aspiration Needle. The modifications are limited to a modification of the sheath and the addition of a “needle stroke limiter” to the handle. The needle and stylet within the sheath, as well as the handle, remain unchanged.
- The **iNod Ultrasound Catheter** is a slightly modified design of the commercially available BSC OptiCross Coronary Imaging Catheter. The modifications are limited to the absence of the distal guide catheter tip beyond the ultrasound transducer and the absence of a hydrophilic coating on the sheath.
- The **iNod Ultrasound Imaging System** and its two accessories, the **iNod Motor Drive Unit** and the **iNod Sled**, are identical to the commercially available BSC iLab Ultrasound Imaging System and its accessories.

The study system is not approved for commercial use. Local IRB (Institutional Review Board) approval will be obtained at each participating center.

All components of the iNod System are labeled as investigational and include information not limited to name of legal manufacturer, device name and dimensions, lot number, expiration date and investigational use statement.

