Imaging to be captured during the iNod System maneuvers, as identified with the serial number of the iNod Imaging System and iNod Biopsy Needle being utilized for each maneuver, will be collected as follows:

- Ultrasound image of the target lesion
- Ultrasound image of the deployed iNod Biopsy Needle at the target lesion
- Supplemental fluoroscopic images, if collected, should also be retained and similarly associated to the specific maneuver by documenting the serial number of the iNod Biopsy Needle being used for that specific procedure

Rapid on-site evaluation (ROSE) will be completed for all obtained specimens. Results will be associated with the serial number of the iNod Biopsy Needle being used for each unique specimen. ROSE interpretations, “adequate (for cytologic evaluation)” or “inadequate (for cytologic evaluation),” will be recorded. Collected specimens will undergo cytologic evaluation following the iNod procedure and final cytologic results will be reported in the study database.

The following situations would indicate the need to abandon the iNod System Procedure and proceed to salvage:

- If the iNod System is unable to physically reach the lesion, as evidenced by the absence of an ultrasound image of the lesion with the iNod System.
- If 3 separate aspirated specimens obtained from the target lesion with the iNod System result in “inadequate (for cytologic evaluation),” the investigator should stop iNod maneuvers and proceed to salvage.

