9.1. Endpoints

9.1.1. Primary Endpoint

Clinical success is defined as the iNod System's ability to acquire adequate specimens of cellular matter suitable for the cytologic evaluation of targeted lung lesions, under real-time visualization. The rate of Clinical Success will be calculated as the number of peripheral pulmonary lesions for which adequate cytologic specimens suitable for cytologic evaluation were obtained divided by the number of lesions the iNod System was attempted.

Hypotheses

There will be no formal statistical hypothesis tested since this is an observational study documenting the first human use of the iNod System

Sample Size

Enrollment is capped at 30 subjects with a maximum of 10 subjects per center. Since no formal hypothesis will be tested, there is no statistical justification of sample size.

Peripheral pulmonary lesions vary in their location in the tracheobronchial tree. Their size, characteristics (e.g., concentric vs. eccentric), and a sample size of 5-10 subjects per site allows greater potential to evaluate the usability and performance of the system for visualization and sampling this range of lesions.

Performance feedback for this traditional feasibility study is sought from more than 1 physician. While staying within the sample size confines of a traditional feasibility study, Boston Scientific has elected to seek the expertise of 2 to 3 interventional bronchoscopists.

Statistical Methods

Since no formal hypothesis is tested, only descriptive statistics will be used to summarize the primary endpoint.

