2.1.3 Statistical Methods

For the primary endpoint of clinical success, the analysis will be performed as described below.

For all PP patients, the primary endpoint of clinical success occurs when there is at least one adequate specimen of cellular matter suitable for the cytologic evaluation of targeted lung lesions is acquired under real-time visualization by the iNod System. If there is no adequate specimen of cellular matter suitable for the cytologic evaluation of targeted lung lesions, under real-time visualization by the iNod System, then the patient will be considered a clinical failure. The primary endpoint will be evaluated as the number of clinical successes out of all PP patients; a 95% exact confidence interval will also be calculated for the primary endpoint.

For patients who do not have clinical success and a salvage procedure is done, the proportion of patients with a salvage procedure for which at least one adequate specimen of cellular matter suitable for the cytologic evaluation of targeted lung lesions will be calculated; a 95% exact

Boston Scientific
iNod Feasibility SAP
91154618 Rev/Ver AA
Page 5 of 11

confidence interval will also be calculated for the proportion of patients with a successful salvage procedure.

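### The SAP 6.3.4 calculation of clinical success omits the visualization condition and drops subjects with a blank adequacy answer, so the primary rate can exceed the one SAP 2.1.3 defines

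*SAP*

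**What the plan says.** SAP 2.1.3 sets two requirements. A success needs at least one adequate specimen that "is acquired under real-time visualization by the iNod System"; a PP patient with no adequate specimen obtained that way is a clinical failure. For the denominator, "The primary endpoint will be evaluated as the number of clinical successes out of all PP patients", with an exact 95% confidence interval.

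SAP 6.3.4 opens with the same definition, visualization included, and then gives the calculation. Its only data points are PP membership and the form item "If yes, was it adequate for Rapid On-Site Evaluation (ROSE) Diagnosis/Cytology". The numerator is PP subjects answered 'Yes'. The denominator is PP subjects answered 'Yes' or 'No'.

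PP membership (SAP 3.2.2 and 6.3.2) requires only that a sample was obtained with the iNod System. It requires neither visualization nor a completed adequacy answer.

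Protocol 9.1.1 shows the same slip within one paragraph. The definition includes real-time visualization, but the rate that follows has as its numerator "the number of peripheral pulmonary lesions for which adequate cytologic specimens suitable for cytologic evaluation were obtained", with no mention of it.

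**The concern.** SAP 6.3 is the section a programmer works from, and the endpoint it produces is not the one defined in 2.1.3. An adequate specimen taken without the needle and lesion in view fails the 2.1.3 definition but is a success under 6.3.4. A PP subject whose adequacy answer is blank belongs in the 2.1.3 denominator but disappears under 6.3.4. Section 2.1.3 does not say expressly how a blank counts, so the two sections conflict without a stated resolution.

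The visualization condition is not incidental. Protocol section 1 presents it as what separates the device from standard radial EBUS, where the sampling device is advanced blindly: "It provides real-time visualization of the biopsy needle and target peripheral pulmonary lesions during tissue acquisition". Section 2 describes the system as "displaying an ultrasound image of the lesion and needle simultaneously". Neither document turns this into a definition of real-time visualization for the endpoint.

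In a single-arm descriptive study, the proportion and its exact interval are the main result. Lesion visualization and needle deployment are secondary endpoints, but they are planned as separate proportions and not joined to adequacy subject by subject. From the planned summaries, a reader could not work back to the defined rate.

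**Working it through.** The plan states no expected rate and no sample-size calculation, so there is no figure of its own to reproduce. The check compares the two written rules.

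**Inputs.** From the documents: the success definition and denominator (SAP 2.1.3), the calculation rule (SAP 6.3.4), PP entry (SAP 6.3.2), the exact 95% interval (SAP 2.1.3, taken as two-sided Clopper-Pearson) and 15 to 30 subjects (SAP Protocol Summary). Assumed: all of them are PP, and 80% of PP subjects have adequacy 'Yes'.

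**Formulas.** Let n = PP subjects, Y = subjects answered 'Yes', u = 'Yes' subjects whose specimen was not visualized, and m = subjects with a blank answer.

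- SAP 2.1.3, with a blank counted as not a success: (Y − u)/n
- SAP 6.3.4: Y/(n − m)

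Since Y − u ≤ Y and n − m ≤ n, it follows that Y/(n − m) ≥ Y/n ≥ (Y − u)/n. The 6.3.4 rate is therefore never the lower one, and the two agree when u = 0 and m = 0. Enumerating all feasible combinations up to n = 30 found no exception.

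**Numbers.** Rates in percent, with exact 95% intervals in parentheses:

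| n | Y | u | m | 2.1.3 rate | 6.3.4 rate | Difference (points) |
|---|---|---|---|---|---|---|
| 15 | 12 | 1 | 0 | 11/15 = 73.3 (44.9–92.2) | 12/15 = 80.0 (51.9–95.7) | +6.7 |
| 15 | 12 | 0 | 1 | 12/15 = 80.0 (51.9–95.7) | 12/14 = 85.7 (57.2–98.2) | +5.7 |
| 15 | 12 | 1 | 1 | 11/15 = 73.3 (44.9–92.2) | 12/14 = 85.7 (57.2–98.2) | +12.4 |
| 30 | 24 | 1 | 0 | 23/30 = 76.7 (57.7–90.1) | 24/30 = 80.0 (61.4–92.3) | +3.3 |
| 30 | 24 | 0 | 1 | 24/30 = 80.0 (61.4–92.3) | 24/29 = 82.8 (64.2–94.2) | +2.8 |
| 30 | 24 | 1 | 1 | 23/30 = 76.7 (57.7–90.1) | 24/29 = 82.8 (64.2–94.2) | +6.1 |

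**Sensitivity to the 80%.** One non-visualized 'Yes' always shifts the rate by 1/n. One blank shifts it by Y/(n − 1) − Y/n = Y/[n(n − 1)]. For n = 15 and Y from 9 to 14 this is 9/210 = 4.3 to 14/210 = 6.7 points. For n = 30 and Y from 18 to 27 it is 18/870 = 2.1 to 27/870 = 3.1 points.

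**Reverse case.** If the blank subject had in truth an adequate, visualized specimen, dropping that subject slightly understates the rate: 12/14 = 85.7% against 13/15 = 86.7%. The upward direction for blanks therefore rests on counting a blank as not a success.

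**The case against.** The strongest reply is that visualization describes how the device samples and is not a separate test. The probe stays in place while the needle is deployed. Protocol 8.5 sends a case to salvage when the lesion cannot be reached, "as evidenced by the absence of an ultrasound image of the lesion with the iNod System". Protocol 9.1.1 computes its rate without the condition, so on the numerator 6.3.4 matches the protocol's own formula. On this reading no adequate specimen lacks visualization. This does not hold against SAP 2.1.3, whose failure sentence repeats the phrase and so makes it a condition of success. The salvage instruction concerns the lesion image only and is not an analysis rule. What stands is that the numerator gap is narrow: mainly lesion seen, needle not seen. Protocol 8.5 also requires "Ultrasound image of the deployed iNod Biopsy Needle at the target lesion", which should make that uncommon.

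Blanks should also be rare. ROSE is to be done on every specimen with its adequacy recorded, and sites must resolve data queries. That bears on frequency and does not remove the conflict, because 6.3.4 writes in an exclusion that contradicts the all-PP denominator.

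Three further points stand. The counts above are assumed. The exact interval at 12/15 is already about 44 points wide (95.7 − 51.9). The case report form is not in the documents, so a usable visualization field may already exist, and images and ROSE results are both tied to the needle serial number. The data link is therefore available; what is missing is its use in the calculation.

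**Conclusion.** The concern holds. SAP 6.3.4 does not implement SAP 2.1.3 in either numerator or denominator, and PP entry repairs neither. The text alone establishes the mismatch; its effect in practice is unknown and is zero if every adequate specimen was visualized and no answer is blank. Under the assumed 80% 'Yes', a single affected subject raises the reported rate by about 6 to 7 points at n = 15 and about 3 points at n = 30; one of each kind raises it by 12.4 and 6.1 points. If the PP set is smaller than 15, one non-visualized 'Yes' weighs more still. No hypothesis, threshold or stopping decision uses the rate, so the consequence is a misreported main result and not a wrong decision. It should be fixed before analysis.

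**What to change.** - **Numerator, SAP 6.3.4.** Require, on the same maneuver as the adequate specimen, a recorded yes/no that lesion and needle were seen in real time. One such maneuver suffices, in line with 2.1.3. Support the answer with the ultrasound images already required, so that an unsaved image alone does not make a failure. List subjects who were adequate but not visualized separately.
- **Denominator, SAP 6.3.4.** Use all PP patients, as in 2.1.3.
- **Missing answers, SAP 2.1.3 and 6.3.4.** State in both that an adequacy answer still missing after query counts as not a success, and report the rate excluding such subjects as a sensitivity result.
- **Protocol 9.1.1.** Add the visualization condition to the rate sentence. That sentence also divides by lesions attempted and not by PP patients, a separate discrepancy that this change does not resolve.

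The cost is SAP and protocol wording, programming, and at most one yes/no item per maneuver on the case report form. The stated rate may be lower. A blank that was in truth a success would count against the device in the main result; the sensitivity rate makes that visible.
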